10.3.2 Quality Control Committee

The PIs (Drs. [name] and [name]) and study coordinator ([name]) will meet monthly to review case report forms and study binders.

10.3.3 Metrics

Spirometry: Subjects will be asked to perform pulmonary function testing for collection of lung function data at each visit. Pulmonary function testing will be performed according to American Thoracic Society (ATS) guidelines (2005). Subjects will be tested using the same spirometry equipment at every visit. Up to 8 efforts will be performed to obtain 3 acceptable and reproducible test results. The best results from the 3 acceptable and reproducible efforts for PFTs will be recorded on the subject's case report form and a copy of the spirometry reports will be retained with the subject's source documents.

Methacholine provocation: The spirometer will be calibrated daily as per ATS guidelines.

10.3.4 Protocol Deviations

Protocol deviations will be captured during subject visits. This will occur by questioning of concurrent medications, appropriate washout of asthma-related medications, pill counts and 2 week recall questionnaires. We will also include less than 70% study drug compliance as a protocol deviation. These will be documented on case report forms. Some deviations (e.g. failure to abide by washout criteria) will result in rescheduling of study visits until the washout period is achieved. Deviations will be review monthly during scheduled meetings of Drs. [name], [name] and the research coordinator. Significant deviations (e.g. failure to comply with consumption of ginger or placebo capsules, failure to appear for study visits within the allowed windows) will result in subject removal from the study.

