6.2.5 Completion/Final Evaluation

Visit 5 Day 71-78 (Day 56 of study drug)

Procedures Performed:

- Administer questionnaires (ACT, QOL, A2WR)
- Review conmeds, and AEs since the previous visit (V4)
- Review study drug compliance (pill count)
- Confirm medication washouts (reschedule if not met).
- GI side effect check list
- Vitals
- Urine Pregnancy Test (if applicable)
- Physical Exam
- Exhale Nitric Oxide (FeNO)
- Spirometry
- Perform Methacholine Challenge --- reschedule visit if FEV₁ is < 60% or 1.5 L
- Administer bronchodilator
- Methacholine Recovery Challenge
- Collect Blood for cytokines, biomarkers and eosinophil count
- Pre-dose Pharmacokinetic blood draw--**PK subgroup only.**
- Study Drug Dosing
- Pharmacokinetic blood draw (Time 0.5, 1, 2, 3, 4 & 8 hrs)—**PK subgroup only.**
- Collect study drug.

Any subjects who discontinue the study early will be contacted to determine the reason why. These reasons will be documented in the study binder. If termination occurs to lack of tolerance or adverse events related to the study drug or procedures, protocols for reporting adverse events will be followed as outlined below.

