8. INTERVENTION DISCONTINUATION

Adverse gastrointestinal events associated with the consumption of ginger that require medical intervention (intravenous fluid administration, hospital admission) will prompt temporary suspension of enrollment and/or study interventions until a complete safety review is convened. Adverse reactions to inhaled methacholine that require hospital admission will prompt temporary suspension of enrollment and/or study interventions until a complete safety review is convened. Subsequent review of serious, unexpected, and related AEs by the DSMB, Independent Safety Monitor(s), IRB or the FDA may also result in suspension of further study interventions/administration of study product. The FDA retain the authority to suspend additional enrollment and study interventions/administration of study product for the entire study, as applicable.

Participants will continue to be followed with their permission if study intervention is discontinued. Temporary discontinuation of treatment would interrupt the consecutive 56 day treatment plan and thus subjects would be removed from the study. If a subject is removed from the study, evaluations related to any adverse events would be continued as defined in section 7.5 above.

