9.3 Definition of Populations

Adults aged 18 years and above, with mild to severe persistent asthma will be enrolled. Subjects will have asthma which is not optimally controlled despite the current use of inhaled corticosteroids with or without inhaled long-acting beta agonists. The populations will be those subjects randomized to the placebo arm versus ginger extract arm.

All randomized subjects will be included in the primary analysis, analyzed based on intention-to-treat. In addition, a secondary analysis based on per protocol will be conducted. Per protocol analysis will exclude patients who missed 30% or more of their assigned treatment. Please refer to section 5.4 for the equation to calculate compliance.

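### Section 10.3.4 removes participants from the study for significant non-compliance or missed visit windows, so the outcomes needed for the Section 9.3 intention-to-treat analysis are not secured

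*Combined protocol and SAP*

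**What the plan says.** Section 9.3 defines the primary analysis: "All randomized subjects will be included in the primary analysis, analyzed based on intention-to-treat". Adherence is left to a secondary analysis: "Per protocol analysis will exclude patients who missed 30% or more of their assigned treatment".

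Section 10.3.4 first treats low adherence as something to record: "We will also include less than 70% study drug compliance as a protocol deviation". It then goes further for deviations called significant, with two examples: "failure to comply with consumption of ginger or placebo capsules, failure to appear for study visits within the allowed windows) will result in subject removal". The removal is from the trial itself. No threshold separates a significant deviation from any other.

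On what happens afterwards:

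- Section 6.2.5: "Any subjects who discontinue the study early will be contacted to determine the reason why". No outcome visit is attached.
- Section 8, on stopping the intervention: "Participants will continue to be followed with their permission if study intervention is discontinued". No assessment is named.
- Section 8, next sentence: "Temporary discontinuation of treatment would interrupt the consecutive 56 day treatment plan and thus subjects would be removed from the study".
- Section 8, last sentence: "If a subject is removed from the study, evaluations related to any adverse events would be continued as defined in section 7.5 above".

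Section 9.6 compares the change in log PD20 between arms by a two-sample t-test, and plans a paired within-patient t-test for FeNO. It gives no method for missing values.

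**The concern.** An intention-to-treat analysis needs outcomes from people who did not follow the protocol. Section 10.3.4 can end outcome collection for just those people, because of what they do after randomisation. The planned contrast between intention-to-treat and per-protocol is weakened, since some of those whom the second set would exclude may have no later value in the first.

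For PD20, the between-arm comparison is biased if the loss is related to outcome and differs between arms. A larger sample does not correct that, and visits not held cannot be recovered later. For FeNO, where only a paired test is planned, the cost is in numbers and in who remains in the pairs.

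The protocol also contains a possible route from lung status to removal. Section 6.2.4 reschedules Visits 4 and 5 when FEV1 is too low, and Section 5.3.1 reschedules a visit when rescue medication falls within a washout. Neither says whether a visit pushed past its window counts as a failure to appear. If it does, participants with worse asthma are more exposed to removal. This is a mechanism, not evidence of a difference between arms.

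**Working it through.** **1. Which data a removal can cost.** Pill counts are taken at the 28 and 56 day visits (Section 5.4). PD20 and FeNO are measured at the same visits (Section 9.5.1).

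| Ground for removal | Found at | Outcome at risk |
|---|---|---|
| Non-compliance | Visit 4 | Day 56 only; Day 28 may already be in hand |
| Non-compliance | Visit 5 | possibly nothing |
| Missed window | Visit 4 | Day 28 and Day 56 |
| Missed window | Visit 5 | Day 56 |

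Nothing says that data already collected are deleted.

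**2. The plan's own sample size.** With SD 0.6, two-sided 0.05 and 80% power, the Section 3 table means give 1.73 − 1.07 = 0.66, or 0.66/0.6 = 1.1 SD. The noncentral t then needs 14.0 per arm, which matches the plan's 14. For FeNO, 37/37 = 1 SD gives 16 per arm by the normal approximation. Attrition: 16/0.9 = 17.8, so 18 per arm and 36 in total. The margin is 36 − 32 = 4 participants, two per arm.

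**3. Power for PD20 as numbers fall.** Two-sample t, two-sided 0.05, noncentrality (δ/0.6)·√(n/2). For example, δ = 0.7 and n = 16 gives 1.167 × 2.828 = 3.30 and power 89%.

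| Per arm | 18 | 16 | 14 | 13 | 12 |
|---|---|---|---|---|---|
| δ = 0.7 (Section 9.2) | 93% | 89% | 84% | 81% | 78% |
| δ = 0.66 (Section 3 table) | 89% | 85% | 80% | 77% | 73% |

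No FeNO power is given, because Section 9.6 plans a paired test there.

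**4. Bias and error for PD20.** The documents give no removal rate, so every rate, correlation and asymmetry below is assumed. So is the choice of Day 56, since Section 9.6 names no single time point for the between-arm test. The setting is 18 per arm, SD 0.6, no drug effect, and a pooled t-test on those with a Day 56 value. Removal follows a latent normal variable with correlation r to poor outcome. Each scenario has 200,000 simulated trials (Monte Carlo SE of the error about 0.05 percentage points).

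The bias can be checked by hand. With a proportion p removed, the mean of those who remain shifts by r × 0.6 × φ(z_p)/(1 − p). For r = 0.5, p = 15% gives 0.5 × 0.6 × 0.2332/0.85 = 0.082, and p = 5% gives 0.5 × 0.6 × 0.1031/0.95 = 0.033. The difference is 0.05 in favour of ginger.

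Case (a), every removed participant loses Day 56 (bias in doubling doses; two-sided error):

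| Loss, ginger/placebo | r = 0.2, both arms | r = 0.5, both arms | r = 0.5, ginger only |
|---|---|---|---|
| 15%/5% | 0.020; 5.1% | 0.049; 5.7% | 0.083; 6.7% |
| 20%/10% | 0.019; 5.1% | 0.046; 5.5% | 0.106; 7.6% |
| 30%/10% | 0.035; 5.2% | 0.090; 6.8% | 0.149; 9.8% |

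With r = 0, or with equal loss (20%/20% or 30%/30%) and equal r, the bias is within 0.001 of zero and the error is about 5%.

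Case (b), half of the removals are found at Visit 5 and lose nothing, so the rates halve:

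| Loss, ginger/placebo | r = 0.2 to 0.5, both arms | r = 0.5, ginger only |
|---|---|---|
| 7.5%/2.5% | 0.012–0.028; 5.0–5.2% | 0.046; 5.5% |
| 10%/5% | 0.011–0.026; 5.1–5.2% | 0.058; 5.8% |

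Halving 30%/10% gives 15%/5%, the first row of case (a).

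**The case against.** The rule is narrower than a quick reading suggests. It applies only to significant deviations, and compliance below 70% is listed merely as a deviation, so removal may be reserved for gross non-compliance. That stands as a possible reading, but the undefined term is part of the problem.

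Much of the data may survive. Non-compliance found at Visit 4 leaves the Day 28 value usable, and found at Visit 5 it may cost nothing. Some who fail to appear would be missing under any rule. Case (a) is therefore an upper bound for the non-compliance ground, and the two analysis sets remain distinct to some degree. All of this stands and limits the size.

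A differential effect is not supported by evidence. Deviations are reviewed by the principal investigators and the coordinator, who are blinded (Sections 6.2.3 and 10.1), and the rule covers both kinds of capsule, so any difference must come from participants' behaviour. The two placebo-controlled 28-day ginger studies in Section 2.2 report no significant excess of adverse events, although this trial runs for 56 days. The 10% attrition in Section 9.2 is an overall figure and may already include removals. These points also stand.

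Finally, Section 8 promises continued follow-up with permission, and its removal sentence may concern a study-wide suspension rather than an individual interruption. This helps only in part: the follow-up sentence names no PD20 or FeNO visit and does not reach the grounds in Section 10.3.4.

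**Conclusion.** The concern holds. Sections 9.3 and 10.3.4 are not reconciled, and no other section secures Visit 4 and Visit 5 outcomes for those removed. Confidence is high for that conflict, not for the size of its consequence.

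Under the assumed rates, loss linked to outcome in both arms gives a bias of 0.02 to 0.09 doubling doses and an error of 5.1% to 6.8% when all removals lose Day 56. If half lose nothing, the range is 0.01 to 0.05 with an error of at most 5.7%. The largest figures, 0.15 and 9.8%, need 30% loss on ginger against 10% on placebo, correlation 0.5, and linkage on ginger only. PD20 power stays at or above 80% down to 14 per arm on either effect size.

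The likely effect is modest, but the lost data could not be recovered and the remedy is cheap. It should be fixed.

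**What to change.** - **Section 10.3.4:** record non-compliance and out-of-window visits as deviations that do not end outcome follow-up. With the participant's permission, still collect Visit 4 and Visit 5 outcomes with their actual dates (PD20 only where the protocol's safety criteria allow), and analyse them in the randomised arm. If any removal is kept, define what makes a deviation significant.
- **Section 6.2.5:** add the same outcome visits for those who discontinue early.
- **Section 9.3:** leave adherence exclusions to the per-protocol analysis, as already planned.
- **Section 8:** reconcile the statements on follow-up and on removal with each other and with Section 9.3. Whether study drug continues is for the sponsor.

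The cost is a short amendment, a few visits for participants off study drug, and slight dilution of the intention-to-treat estimate. Participants who decline follow-up will still lack values, and Section 9.6 has no method for them; this change reduces that gap but does not close it.

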10.3.5 Monitoring

Data type	Frequency of review	Reviewer
Subject accrual (including compliance with protocol enrollment criteria)	Monthly	PIs & research study coordinator(s)
	Semi-annually	Independent Monitors [name] & [name], PhD
Status of all enrolled subjects, as of date of reporting	Monthly	PIs & research study coordinator(s)
	Semi-annually	Independent Monitors [name] & [name], PhD
Data entry quality control checks on 5% of charts	Quarterly	[name] (departmental clinical compliance coordinator)
Adherence data regarding study visits and intervention	Monthly	PIs & research study coordinator(s)
Adherence data regarding study visits and intervention AEs and rates (including out-of-range lab values)	Semi-annually	Independent Monitors [name] & [name], PhD
	Monthly	PIs & research study coordinator(s)
AEs and rates (including out-of-range lab values) SAEs (unexpected and related)	Semi-annually	Independent Monitors [name] & [name], PhD
	Annually	NCCIH, FDA (If Applicable)
	Per occurrence	PIs & Independent Monitors [name] & [name], PhD NIH/NCCIH, FDA (if applicable)
SAEs (expected or unrelated)	Per Occurrence	PIs & [name] (departmental clinical compliance coordinator)
SAEs (expected or unrelated) Unanticipated Problems	Annually	Independent Monitors [name] & [name], PhD NIH/NCCIH

	Monthly	PIs & research study coordinator(s)
Unanticipated Problems	Per Occurrence	IRB, FDA (if applicable)

11. PARTICIPANT RIGHTS AND CONFIDENTIALITY

11.1 Institutional Review Board (IRB) Review

This protocol and the informed consent document and any subsequent modifications will be reviewed and approved by the IRB for oversight of the study. The consent form is separate from the protocol document.

11.2 Informed Consent Forms

A signed consent form will be obtained from each participant. Consent forms are available in the English and Spanish language. The consent form describes the purpose of the study, the procedures to be followed, and the risks and benefits of participation. A copy will be given to each participant and this fact will be documented in the participant's record.

11.3 Participant Confidentiality

Participant data, which includes identifiable personal health information (PHI), will be collected at the clinical site. PHI will be stored in accordance with HIPAA regulations and local university and hospital policies. This includes the storage of PHI in locked cabinets or rooms, limited access to secure data areas by certified study personnel, password protection for electronic medical records, and explanation of HIPAA regulations on the study consent form. Analytic files will not contain personal identifiers (e.g. name, address). Reports/manuscripts will be prepared in such a way that individual participants cannot be identifiable.

Data such as lung function or laboratory tests that are collected as part of this study may be transmitted to the participants treating physicians with the consent of the participant. Participants will be informed in the consent that PHI may also be disclosed for auditing purposes by the NIH or other regulatory bodies and is subject to subpoena.

Personal identifiers (e.g. name, address, EMR number) are not transmitted to the Data and Safety Monitor or central laboratory in that all biospecimens and records are identified by a study ID, and other identifying information such as names are not entered into the central study database. Source records that are transmitted to the Data and Safety monitor for data quality audits have identifying information redacted. No highly confidential information is routinely collected, although the data collection does include PHI, so a breach of confidentiality would constitute a HIPAA violation.

We will advise participants that the U.S. Department of Health and Human Services has the right to inspect medical records relating to this research for the purposes of verifying data. Where data are shared with other research entities, it will comply with the HIPAA definition of a limited dataset, and appropriate IRB approvals and waivers will be obtained.

11.4 Study Discontinuation

The study may be discontinued at any time by the IRB, the NCCIH, the OHRP, the FDA, or other government agencies as part of their duties to ensure that research participants are protected.

12. COMMITTEES

The PIs ([name] and [name]) will be responsible for the overall conduct of the study, data management, data analysis, publications and reports to respective committees (IRB, FDA, NCCIH, DSMB).

A Data Safety Monitoring Board consisting of two individuals not affiliated with the study and without

conflicts of interest with the PIs will meet with the PIs semi-annually or per occurrence for adverse events to review documents as detailed in the table above in section 10.3.5.

13. PUBLICATION OF RESEARCH FINDINGS

Any presentation, abstract, or manuscript will be made available for review by the NCCIH prior to submission.

15. SUPPLEMENTS/APPENDICES

Consent Form

Case Report Forms
